### PICOTS

**Population:** All Danish citizens who have received a primary knee arthroplasty at a Danish healthcare facility, from the 1st of January 1998 to the 31st of December 2021

**Intervention/Exposure** Multiple revision knee arthroplasties in the same knee

**Comparator:** None

**Outcome (primary):** Annual standardized prevalence and incidence of n-grade revisions following knee arthroplasty between 1998 and 2021 in Denmark.

**Time:** Retrospectively, from the 1st of January 1998 to the 31st of December 2021, i.e., up to 24 years follow-up.

**Study design:** Observational retrospective register study.

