#### **Data management, for both registers.**

Definition of a revision: A revision is defined as the exchange, addition, or removal of a knee prosthesis component (1). However, knee arthrodesis and amputation are not included in this study.

Definition of major revision: A major revision is defined as exchange of the femoral component and/or the tibial component with subgroups of tibial, femoral and all component exchange (2).

Definition of minor revision: A minor revision is defined as the exchange of polyethylene liner and/or addition or revision of the patella component. Insertion/removal/exchange of spacers are also included in this category (2).

Population: The population is defined as the number of alive citizens in the state of Denmark. Annual populations are defined as the population in Denmark on the 1st of January that year. Additional data for sex and age of the population is acquired. Data for the population is acquired from Danmarks Statistik (3).

In case of disagreement between registers: In cases of discrepancy between the two registers, Landspatientregisteret will overrule the Danish Knee arthroplasty register concerning following variables:

- Laterality
- Date of surgery
- Gender
- Age
- Performing institution

In cases of discrepancy between the two registers, the Danish Knee arthroplasty register will overrule Landspatientregisteret concerning following variables:

- Procedure code
- Revision of tibia
- Revision of femur
- Indication

Calculation of standardized prevalence: Annual standardized prevalence is calculated as the number of patients living with a n-grade revision during a given year as a proportion of the population in Denmark (the 1st of January that year) (3). The prevalence is then multiplied by 100,000 for standardization. This is done for each level of revision, each year. E.g., the standardized prevalence for 1998 is calculated as:

$$\text{Standardized prevalence, 1998} = \frac{\text{Number of knees living in 1998 with a } n - \text{ grade revision}}{\text{Total population in Denmark in 1998}} * 100,000$$

The prevalence is only calculated for revisions performed between January 1st 1998 and December 31st 2021.

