Calculation of standardized incidence: Annual standardized incidence is calculated as the number of new n-grade revisions performed as a proportion of the population in Denmark during a specific year. The population size of Denmark is defined as the population size at January 1st for that year (3). The incidence is then multiplied by 100,000 for standardization. This is done for each level of revision, each year. E.g., the standardized incidence for 1998 is calculated as:

$$\text{Standardized incidence, 1998} = \frac{\text{Number of new } n - \text{ grade revisions in the population in 1998}}{\text{Total population in Denmark in 1998}} * 100,000$$

Missing data: We expect to encounter some missing data. All missing data will be described.

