Year	1 st revision	2 nd revision	....	n grade revision	Maximal grade of revision performed*
1998					
1999					
2000					
2001					
2002					
2003					
2004					
2005					
2006					
2007					
2008					
2009					
2010					
2011					
2012					
2013					
2014					
2015					
2016					
2017					
2018					
2019					
2020					
2021					

Only grades of revisions with occurrences >10 for all years are shown

\*The maximal grade of revision performed is defined as the single greatest grade of revision performed that year

[figure not shown]
**Figure 2.** The standardized prevalence and incidence rates of n-grade revisions from 1998 to 2021.

*Anticipated plot design, illustrating with imaginary data, A-D*

Panel A and B illustrates standardized prevalence and incidence of major n-grade revisions. Panel C and D illustrate standardized prevalence and incidence of all n-grade revisions (including both major and minor revisions). Only grades of revisions with occurrences >10 are shown; for prevalence, >n-grade revisions are reported as well.

**Figure 3.** The standardized prevalence of patients with their total sum of revisions.

Panel A illustrates standardized prevalence of patients with major n-grade revisions. Panel B illustrates standardized prevalence rates of patients with all n-grade revisions (including major and minor revisions). The total sum of revisions is the summation of all revision procedures performed on a patient. E.g., a patient with 3 revisions performed on one knee and 4 revisions performed on the other knee, is categorized as a 7-grade revision patient. Only grades of revisions with occurrences >10 are shown as well as >n-grade grade revisions.

[figure not shown]

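### The primary outcome is labelled 'standardized' but is a crude figure per 100,000, and no annual series holds age and sex fixed

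*SAP*

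**What the plan says.** SAP section 1 (PICOTS) gives the primary outcome as "Annual standardized prevalence and incidence of n-grade revisions following knee arthroplasty between 1998 and 2021 in Denmark". Section 3 defines both measures as a count divided by the total population on 1 January of that year. For prevalence it then says "The prevalence is then multiplied by 100,000 for standardization", and for incidence "The incidence is then multiplied by 100,000 for standardization".

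The label recurs in the captions of Figure 2 ("The standardized prevalence and incidence rates of n-grade revisions from 1998 to 2021"), Figure 3 ("The standardized prevalence of patients with their total sum of revisions") and Supplementary Figures 1-10. Supplementary Tables 1-4 head their columns simply per 100.000. The Protocol (Statistics, WPA1) defines incidence and prevalence as proportions of the current year's population without calling them standardized.

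On age and sex, SAP section 3 says "Additional data for sex and age of the population is acquired". The supplement plans annual series by sex (all ages together), annual series for ages 18-49, 50-69 and 70-99 (sexes together), and tables crossing age with sex for 2021 only. In the SAP's reporting checklist, the item on covariate adjustment points to section 5, which contains none, and the item on confounding covariates is marked with a dash.

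**The concern.** In epidemiology, a standardized rate is one weighted to a fixed reference population so that changes in age and sex structure drop out. Multiplying by 100,000 does not do that. The study describes a trend over 24 calendar years and plans no tests or confidence intervals, so the displayed series are the result. Captions and a primary-outcome statement are often read without the methods text. A reader who takes the word in its usual sense would think that a rise in Figure 2 could not be due to an older population.

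The question is a natural one here. The Protocol's Background presumes that a growing share of elderly people helps to drive the need for knee surgery, and WP-A1 aims to predict future incidence and prevalence from demographic data.

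**Working it through.** **1. What the formula gives.** Measure = count / total population that year x 100,000. The Protocol reports 1,048 revisions of all grades in 2020. The documents give no population figure; assuming 5.5 to 6.0 million, the result is 1,048/5,500,000 x 100,000 = 19.1 down to 1,048/6,000,000 x 100,000 = 17.5. The factor 100,000 cancels in any ratio between two years, so it changes the unit and nothing else.

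**2. What is missing.** Direct standardization would be 100,000 x the sum over strata of (stratum count / stratum population that year) x (stratum share in a fixed reference population). The SAP names no reference population, strata or weights for this purpose, and no planned table or figure combines the strata into one annual value.

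**3. How far ageing alone could move the crude value.** Every input here is assumed; none is a Danish figure from the documents. Stratum rates are held constant over time, so the directly standardized ratio is 1.00 throughout. Crude ratio = sum(rate x later share) / sum(rate x earlier share), for ages 0-17, 18-49, 50-69 and 70+.

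| Age shift | Earlier shares | Later shares | Relative rates | Crude ratio |
|---|---|---|---|---|
| Small, no adult gradient | .215, .46, .22, .105 | .205, .435, .24, .12 | 0, 1, 1, 1 | .795/.785 = 1.013 |
| Small, weak gradient | same | same | 0, 1, 1.5, 1.5 | .975/.9475 = 1.029 |
| Larger, steep gradient | same | .195, .395, .26, .15 | 0, .2, 3, 12 | 2.659/2.012 = 1.322 |
| Largest tried, steep gradient | .22, .46, .225, .095 | .19, .39, .265, .155 | 0, 1, 25, 90 | 20.965/14.635 = 1.433 |

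The range tried is therefore about 1% to 43%. Its width reflects the assumptions; it says nothing about Denmark.

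**4. Which reference population.** SAP section 1 sets no age limit: "All Danish citizens who have received a primary knee arthroplasty at a Danish healthcare facility". If the adjusted line used a reference limited to ages 18-99 while the crude line kept the whole population, the two would disagree even in the reference year. With 19.5% to 20.5% of people outside that range (assumed) and no revisions among them, adjusted/crude in 2021 would be 1/(1 - .195) = 1.242 to 1/(1 - .205) = 1.258. With strata covering all ages and 2021 weights, the ratio is 1.000.

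**5. Precision.** For age weights w = later share / earlier share and expected counts d, the relative SE of the standardized value is sqrt(sum w²d) / sum(wd), against 1/sqrt(sum d) for the crude value. For the 1998-type shares in the first row of step 3, the ratio of the two runs from 1.001 to 1.021 over the gradients tried. That covers four age bands without sex; six age groups by sex, on separate assumed inputs, cost about 1% to 1.5%.

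The counts matter far more. Take 1,048 revisions and assume that each grade is 20% of the one before, a loose use of the 20% steps that the Protocol cites from the English register.

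| Grade | Count | 95% Poisson limits |
|---|---|---|
| 1 | 1,048 x .8 = 838 | -7% / +7% |
| 2 | 838 x .2 = 168 | -15% / +16% |
| 3 alone | 168 x .2 = 34 | -31% / +40% |
| 3 or more | 1,048 x .04 = 42 | -28% / +35% |

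**The case against.** The SAP defines the word where it uses it and prints the total population as the denominator, so no planned number is wrong and a careful reader of section 3 is not misled. The study is descriptive, with no comparator and no testing, and its hypothesis concerns number and burden, for which a crude value is the right measure. The supplement already shows whether rates change within each age band and each sex. The Protocol's remark on ageing concerns the need for knee surgery in general, and the prediction model is not an objective of this SAP.

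Most of this stands. It means that the crude series must be kept and that the adjusted series is an addition, not a replacement. It does not rescue the label, because the outcome statement and captions claim a property that the measure lacks. Nor do the supplementary figures supply the missing summary: the bands are wide, age is not crossed with sex over time, and grades with 10 or fewer occurrences are not shown.

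A reader might infer that the primary analysis is invalid, that the SAP ignores age and sex, or that any rise found will be an artefact of ageing. The documents support none of these. They give no age-specific rates or age shares from which the contribution of ageing could be judged.

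**Conclusion.** The point holds as a labelling error in the primary outcome, together with a gap in the planned displays. The labelling error is certain from the formulas and needs no assumptions. The gap is that nothing planned separates a change in population structure from a change in the rate at a given age and sex in one annual series. Its practical size is unknown: the 1% to 43% range rests wholly on assumed age shares and rate gradients, and the low end is not a floor, since a smaller age shift would give less.

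An adjusted series would not settle every question about the trend. The SAP states "The prevalence is only calculated for revisions performed between January" 1998 and 2021, so prevalence accumulates from a truncated start. Where grade is counted only from primaries performed since 1998, n-grade incidence also builds up in the early years. Age and sex weighting removes neither effect.

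**What to change.** 1. **Relabel.** Use 'crude prevalence per 100,000 population' and 'crude incidence per 100,000 population' in the primary outcome, both definitions in section 3 and the captions of Figures 2 and 3. In Supplementary Figures 1-10 use 'sex-specific' or 'age-specific' prevalence and incidence, per 100,000 of that stratum's 1 January population. Plain 'crude rate' would not fit everywhere: prevalence is a proportion, and the age-band figures are age-specific.

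2. **Add one series to Figure 2**, beside the crude one: directly standardized by age and sex, weighted to the whole Danish population on 1 January 2021. Let the strata cover all ages (for example 0-17, 18-49, 50-59, 60-69, 70-79 and 80 or over, by sex), so that the two lines meet in 2021. Use attained age for prevalence. Show grade 1, grade 2 and grades 3 or more pooled, which is the SAP's own multiply revised group, with annual counts and under the existing rule of more than 10 occurrences.

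3. **State the limit.** Say that standardization does not remove the early build-up in prevalence or, where grade is counted only from primaries since 1998, in n-grade incidence.

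The cost is a few lines of text and a little code. Population data by sex and age are already acquired, although their band width is not stated. The downside is instability at sparse grades, which comes mainly from the small counts; on assumed inputs the weighting itself adds about 2% or less to the relative SE.

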Landspatientregisteret (LPR) is a national and clinical database administered by the Danish Health Authority since 1976. All information generated when a patient is treated by the public health service is reported here. In addition to information regarding procedures and admissions, the register contains information on residence, partner status, level of education, income, comorbidities and emigration amongst others. Operations are recorded according to the NOMESCO classification, while diagnoses are coded according to the ICD-10 classification.

Identification of primary procedures

We will determine the cohort of primary procedures from DKR (called P-DKR) by identifying all primary procedures performed from January 1st 1998 to December 31st 2021. P-DKR is then transferred to Danmarks Statistik (DS). Through DS, all primary procedures in the observation period will be identified using NOMESCO operation codes (KNGB*) and these will be collected in a cohort called P-SD. P-DKR and P-SD will be joined into a cohort called PRIM and this cohort will best describe all primary procedures performed in Denmark during the observation period.

Identification of revision procedures

The DKR cohort of revisions (R-DKR) will be identified by all registrations marked as revisions during the observation period. R-DKR is also transferred to DS. All revisions will be identified in DS as R-DS using the NOMESCO operation codes KNG* (knee procedure), KNGC* (revision of knee), KNGG* (arthrodesis) and KNFQ19 (femur amputation). The cohorts R-DKR and R-DS will be combined and called REV. This cohort will best describe revision procedures performed in Denmark during the observation period.

Insertion of cement spacers presents a special registration problem, as different registration practices exist. Some use KNGS codes (eg KNGC59A – Insertion of spacer in a knee joint in connection with revision). We intend to not consider spacer insertion as a revision. For example a two-stage revision will be considered as one revision.

Organization of data

A table (G) with PRIM and REV will be created. G will contain information on revisions, deaths, disappearances, emigration and the associated dates. For each knee joint in PRIM and for each date in the observation period, it will be possible to describe the status of the knee joint.

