## 1. STUDY OVERVIEW

---

**Background and rationale** Knee arthroplasty is a common procedure performed worldwide to improve the quality of life for patients with degenerative knee conditions, trauma, and tumours. Complications can occur after knee arthroplasty, which may lead to a revision procedure, where at least one implant is exchanged, added, or removed. As the number of primary procedures in the world is increasing, so is the corresponding number of revisions. Some patients may require additional revision procedures, and some may end in a negative spiral of repeated revisions; We define three or more revisions on the same knee as being 'multiply revised'. The clinical impression of multiply revised patients is that the repeated occurrence of complications has significant impacts on the patients' quality of life including chronic pain, decreased independence, and increased morbidity. No study has yet investigated the incidence and prevalence of multiply revised knee arthroplasty patients stratified by previous revisions. To improve the care of multiply revised patients, epidemiological information is required which is the rationale of this study.

**Objectives** The aim of this observational study is to investigate the incidence and prevalence of multiply revised knee arthroplasty patients in all Danish patients with primary knee arthroplasty.

**Hypothesis** The number and burden of knee arthroplasty revision procedures and patients in Denmark has increased dramatically in the last 23 years.

**Methods** This is an observational study. Data will be collected from all primary and revision knee arthroplasties performed in Denmark from January 1st 1998 to 31st December 2021. Data will be acquired from two registers: The Danish Knee Arthroplasty Register (DKR), containing surgeon-reported data on primary and revision knee arthroplasties. In addition, data will be acquired from Landspatientregisteret, which contains all clinical data collected during any visit to a public or private healthcare facility in Denmark.

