**Figure 1. Flow diagram**

*Anticipated plot design, illustrating potential reasons for exclusion:*

**Table 1.** Characteristics of primary knee arthroplasty procedures.

Characteristics	Primary knee arthroplasties (n = )
Age, years	
Females, n (%)	
Implant type, n (%)	
- TKA	
- Medial UKA	
- Lateral UKA	
- Patellofemoral UKA	
- Unspecified UKA	
- Rotating hinge prosthesis	
- Rotating hinge prosthesis with condyle resection	
- Resection prosthesis	
- Partial resurfacing	
- Unspecified implant type (KNGB09, KNGB14, KNGB99)	
- Isolated patella	
Region for the procedure, n (%)	
- Northern Region of Denmark	
- Middle Region of Denmark	
- Southern Region of Denmark	
- Zealand Region of Denmark	
- Capital Region of Denmark	
- Private hospitals	
- Unknown	
Indication for the primary procedure, n (%)	
- Idiopathic knee osteoarthritis	
- Secondary knee osteoarthritis	
- Sequelae following tibia condyle fracture	
- Sequelae following femur condyle fracture	
- Sequelae following patella fracture	
- Rheumatoid arthritis	
- Sequelae following other arthritis	
- Haemophilia	
- Primary bone tumour	
- Metastatic bone tumour	
- Unknown	
Duration of the procedure, minutes	

Values are means (SD) unless otherwise stated.

Abbreviations: TKA = total knee arthroplasty. UKA = unicompartmental knee arthroplasty

*Further statistical information related to table 1:*

Data will be presented as mean with standard deviation (SD) when normally distributed or as median with interquartile range in case of skewed data. Dichotomous and categorical data will be presented in proportions. Normality of the data will be assessed using Q-Q plots, and histograms.

**Table 2.** Annual occurrence of primary procedures and major n-grade revisions.

Year	Primary procedures, n	1 st revision, n	2 nd revision, n	....	n grade revision, n	Maximal grade of revision performed*
1998						
1999						
2000						
2001						
2002						
2003						
2004						
2005						
2006						
2007						
2008						
2009						
2010						
2011						
2012						
2013						
2014						
2015						
2016						
2017						
2018						
2019						
2020						
2021						

Only grades of revisions with occurrences >10 are shown

\*The maximal grade of revision performed is defined as the single greatest grade of revision performed that year

**Table 3:** Annual occurrence of all n-grade revisions (including both major and minor revisions).

[figure not shown]

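### Prevalence counts only revisions from 1998, so the rise the SAP expects is partly built in by the observation window, most in the early years and for grade 3 or higher

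*SAP*

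**What the plan says.** Under the calculation of standardized prevalence, SAP section 3 states: "The prevalence is only calculated for revisions performed between January 1" 1998 and 31 December 2021. SAP section 2 takes both registers from the same date. The denominator for prevalence and incidence is the total population on 1 January of each year.

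The primary outcome (PICOTS) is the annual series of both measures by grade. The hypothesis in SAP section 1 is: "The number and burden of knee arthroplasty revision procedures and patients in Denmark has increased dramatically in the last 23 years". Table 2 ("Annual occurrence of primary procedures and major n-grade revisions"), Table 3 and Figure 2 start in 1998.

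Which knees enter is not settled in the visible text.

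- **Reading A, only knees with a primary from 1998.** PICOTS defines the population as "All Danish citizens who have received a primary knee arthroplasty at a Danish healthcare facility, from the 1" January 1998 onwards, and the protocol's combined table follows status "For each knee joint in PRIM and for each date in the observation period", where PRIM is the 1998–2021 primary cohort.
- **Reading B, all revisions in the window.** The SAP Methods paragraph says "Data will be collected from all primary and revision knee arthroplasties performed in Denmark from January 1st 1998 to 31st December 2021", and the protocol's register cohort of revisions "will be identified by all registrations marked as revisions during the observation period".

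The wording leans towards A. The flow diagram ("Anticipated plot design, illustrating potential reasons for exclusion") is not reproduced in the copy reviewed and may state the rule.

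**The concern.** The case definition changes over calendar time. At the end of 1998 a living knee can count as grade 3 only if all three revisions fell in that one year. At the end of 2021 the three may be spread over 24 years. The rising part of this fill-up points the same way as the hypothesis.

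The SAP plans no formal testing and treats confidence intervals as not applicable, so the conclusion will be read off the curves. A flat true prevalence would also appear as an increase. The grade affected most, three or more revisions, is the study's own definition of a multiply revised knee. SAP section 3 states the restriction but not its consequence. The visible text has no run-in, look-back, restricted trend period or caution.

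**Working it through.** **The plan's own figures.** The SAP gives no expected prevalence or count to reproduce. The window does check: 2021 − 1998 + 1 = 24 years, as PICOTS says. History available at year-end is 1 year (1998), 6 (2003), 11 (2008) and 24 (2021). The direction of the effect follows from this alone.

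**Inputs from the protocol.**
- First revision: 13% at 20 years (Size of the problem).
- Second, third and fourth revision: 20% at 13, 5 and 3 years (Re-revision; an English register).
- More than 150,000 primaries in 20 years, about 10,500 in 2020 (Background).
- More than 20,000 revisions in 20 years (Size of the problem), kept as a check.

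**Assumed.**
- Weibull shape k of 0.6, 0.8 or 1.0.
- Mortality of 3%/yr, 5%/yr or age-dependent (mean age 68, SD 9.5; 1.3%/yr at 65, doubling every 7.5 years).
- Grades 5–6 behave as grade 4.
- Volume linear from 4,500 (2001) to 10,500 (2020): 20 × (4,500 + 10,500)/2 = 150,000. The slope is 6,000/19 ≈ 316 per year, which reaches zero about 14 years before 2001, in 1987.

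**Formulas.** With risk p at time t, the Weibull scale is t / (−ln(1 − p))^(1/k). For k = 1 the yearly hazards are 0.1393/20 = 0.0070 for the first revision, then 0.2231/13 = 0.017, 0.2231/5 = 0.045 and 0.2231/3 = 0.074. Captured share = counted / true. Spurious factor = (counted 2021 / counted start) / (true 2021 / true start).

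**Results** of a Monte Carlo simulation over the nine shape and mortality combinations (captured share, %):

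| Series | 1998 | 2003 | 2008 | 2021 | Spurious factor to 2021, from 2003 / from 2008 |
|---|---|---|---|---|---|
| B, prevalence grade 1 | 25–28 | 76–81 | 90–94 | 98–100 | 1.2–1.3 / 1.06–1.09 |
| B, prevalence grade 2 | 5–10 | 57–63 | 81–84 | 96–99 | 1.6–1.7 / 1.16–1.20 |
| B, prevalence grade 3 | 0–6 | 37–50 | 71–75 | 94–97 | 1.9–2.6 / 1.29–1.37 |
| B, incidence grade 1 | 106–108 | 102 | 101 | 100 | – |
| B, incidence grade 2 | 15–35 | 81–89 | 94–98 | 99–100 | – |
| B, incidence grade 3 | 0–15 | 59–75 | 84–90 | 97–99 | – |
| A, incidence grade 1 | 10–27 | 62–81 | 80–91 | 95–99 | – |
| A, prevalence grade 3 | 0–2 | 11–25 | 29–50 | 67–87 | 3.3–7.2 / 1.7–2.7 |

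For grade 3 on B, 94/50 ≈ 1.9 and 97/37 ≈ 2.6, which matches the factor from 2003. First-revision incidence on B exceeds 100% because some later revisions are graded as first. Grade 3 shares for 1998–2003 carry simulation noise of a few points.

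**Sensitivity** (grade 3 prevalence captured in 1998/2003/2008/2021).
- *Calibration.* The model gives about 9,700–14,200 revisions in 2001–2020, below the protocol's 20,000. Raising all revision hazards 1.35- to 1.89-fold to reach about 20,000 changes little: 1–4/46–54/75–83/95–99% on B and 0–1/10–25/31–52/71–88% on A.
- *Older stock* (flat 3,550 primaries a year, 1975–97), B: 0–1/11–18/33–44/74–92%.
- *Flat truth* (7,500 a year, age-dependent mortality; a check of mechanism only), B: 0–1/11–16/35–40/86–88%.
- *Separately built model*, all revisions counted, mortality 2–8%, constant or lower volume before 1998: 8–21% of grade 1, 1–7% of grade 2 and 0–2% of grade 3+ prevalence captured in 1998; 43–88% of grade 3+ in 2021. The direction and the ordering by grade held in every run.

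**The case against.** The restriction is disclosed and no test is planned. Beyond that, the strongest points are these.

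- **Not every series is biased upwards.** On Reading B the yearly total of revisions is complete, and first-revision incidence is overstated early, which works against apparent growth. This stands. The concern covers prevalence by grade and incidence of grade 2 and higher, plus first-revision incidence on A.
- **On Reading A the count is complete for its own cohort.** This is true, but the rate is divided by the whole population and presented as the burden in Denmark. A cohort still accumulating members rises whatever happens to the burden.
- **Real growth may dominate.** In the linear model true grade 1 prevalence rises about 5-fold from 2003 to 2021, against a spurious factor of 1.2–1.3 on B; from 2008 it is about 2.8 against 1.06–1.09. This stands for grade 1 on B, although the model's growth partly reflects assuming no primaries before 1987. It does not carry over to grade 3, or to A.
- **The rule of showing only occurrences above 10 hides the worst points.** Counted living grade 3 knees in the unscaled linear model number 0 in 1998 and 0–3 in 2000. This mitigates, but pooled prevalence above the highest displayed grade is still plotted.
- **The sizes are unstable.** They are: for 2021, grade 3+ capture on B is 92–96% in the linear model and 43–88% in the separate one. Confidence attaches to direction and ordering, not to any one percentage.

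**Conclusion.** The concern holds and should be resolved before the analysis is run. Carried out as written, the plan yields a prevalence trend for every grade, and an incidence trend for grade 2 and higher, that rise partly by construction. The effect is largest in the early years and for grade 3 or higher.

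On Reading B with linear volume, incidence of grades 1–2 is close to complete from about 2008 and the 2021 snapshot is little affected; a large stock of older knees would make capture worse. On Reading A, grade 3 prevalence is still under-captured in 2021. The sizes rest on assumed mortality, hazard shape and pre-1998 volume, and on later-grade risks from another country. A genuine increase may exist as well; the planned figures cannot separate the two.

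**What to change.** 1. Label overall prevalence as left-truncated and a lower bound. Do not use 1998 or the early years as baseline for the hypothesis. Attach an explicit caution to any trend statement on grade 3 or higher.
2. Keep the planned series and add a trend for 2008–2021 with equal look-back: knees with a primary in the previous 10 years and, if all revisions are kept, knees with at least n revisions in the previous 10 years. In the flat-truth model both stay flat for at least one revision (2021/2008 ratio 0.996–1.005), while the planned series on Reading B rises 1.34- to 1.42-fold. In a further flat-volume run at 4%/yr mortality, the primary-based look-back was also flat, within noise, for three or more revisions, while planned grade 3+ prevalence rose about 3- to 5-fold.
3. State whether revisions of pre-1998 primaries are included. If they are, add the DKR count of earlier revisions, which the protocol lists as acquired, to the SAP variable list, and use it as starting grade in a sensitivity analysis of the all-revisions series. This is partial: it corrects nothing on Reading A, exists only for procedures recorded in DKR (mandatory only from June 2006), has no major/minor split as listed, so does not serve Table 2 or Figure 2 A–B, and misses knees revised before 1998 and not operated on again.

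**Cost.** SAP wording and some coding; no new data. The trend window is shorter and counts are small. In the linear model the primary-based look-back keeps 5–29 knees with three or more revisions in 2008 and 13–53 in 2021; the revision-based one keeps 15–51 and 55–132. With rates scaled to 20,000 revisions these become 28–70 and 52–134, and 86–120 and 282–385. Under the display rule, the grade 3+ look-back may be shown only overall, or not at all. A pre-1998 register extract is optional and would need a new data request.
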